#### 8.4.2. Prohibited Medications

The use of any antipsychotic other than study drug is prohibited except when subjects are tapering off of current medication (see [Section 8.1](#)). Prohibited medications include the following:

- Monoamine oxidase inhibitors (eg, phenelzine, tranylcypromine, selegiline, or moclobemide)
- Long-acting formulations of any antipsychotic agent
- Antipsychotic agents (with the exception of cross-tapering of previous antipsychotic during first 2-weeks post randomization)
- Use of antipsychotic sleep aids (eg, Seroquel®) is prohibited. However, use of benzodiazepines to treat some symptoms is permissible (see [Section 8.4.3](#))
- In general, the use of psychotropic medications other than study drug is prohibited with the exception of the following (these medications should only be administered after all assessments have been completed for that visit):
  - Beta-blockers (eg, propranolol or pinodolol), antihistamines, and anticholinergics may be used for treatment-emergent akathisia
  - Anticholinergics may be used for extrapyramidal symptoms
- Chantix® (varenicline) is prohibited. However, nicotine replacement therapy including nicotine replacement patch and oral nicotine gum is permitted
- All prescription or over-the-counter (OTC) agents taken for the purpose of weight reduction
- Systemic steroids administered by oral, intravenous, or intramuscular route
- Topiramate (Topamax®) and combination products containing topiramate; Calcitonin (eg, Miacalcin®)
- Diabetes treatments and hypoglycemic agents including Metformin and Insulin
- Antidepressants that have been started within 30 days of screening are prohibited. An antidepressant should not be started during a subject's participation in the study. Subjects who have been on a stable dose of an antidepressant for at least 30 days before screening may be allowed to participate in the study if it is anticipated that the dose will not change during the subject's participation in the study

Medications that are contraindicated with olanzapine use or exhibit drug-interaction potential with olanzapine are prohibited.

Use of moderate to strong inducers or inhibitors of cytochrome P450 (CYP) 3A4 (prescription medications, OTC medications, or dietary supplements) within 30 days before randomization through follow-up is prohibited. Refer to [Appendix A](#) for a list of CYP3A4 inhibitors and inducers.

The CRO medical monitor should be consulted for any questions about use of any psychotropic medications during a subject's participation in this study.

Use of opioid agonists (eg, codeine, oxycodone, tramadol, or morphine) within 14 days before screening is prohibited. Use of opioid antagonists, including naltrexone (any formulations) and naloxone within 60 days before screening and throughout the study period is prohibited. **Note:** during the study period, opioid agonists should be avoided as they may be rendered ineffective by samidorphan.

#### **8.4.3. Permitted Therapy**

Permissible potential medications to treat extrapyramidal symptoms may include benzodiazepines, antihistamines, and anticholinergics. Benzodiazepines should be utilized for treatment-emergent akathisia. While insomnia may be treated with a variety of agents, short half-life benzodiazepines should be utilized to avoid the potential for lingering effects on daytime functioning and study assessments (eg, triazolam). Non-benzodiazepine medication may be used to treat insomnia (eg, zolpidem, eszopiclone). Treatment of agitation and/or anxiety with benzodiazepines is permissible. However, doses should be restricted to no more than a 2 mg lorazepam equivalent per day and should be kept as stable as possible throughout study so as not to interfere with daytime functioning and study assessments.

#### **8.4.4. Pain Management**

Because ALKS 3831 contains samidorphan, a  $\mu$ -opioid receptor antagonist, patients may experience reduced or ineffective analgesia when taking an opioid analgesic agent concurrently with ALKS 3831, including several days after last dosing of ALKS 3831.

In the event of an emergency, pain management of the subject should include the following:

- Regional analgesia or use of non-opioid analgesics
- If opiate anesthesia or analgesia is required, the subject should be continuously monitored, in an anesthesia care setting, by persons not involved in the conduct of the surgical or diagnostic procedure. The opioid therapy must be provided by individuals specifically trained in the use of anesthetic drugs and the management of the respiratory effects of potent opioids, specifically the establishment and the maintenance of a patent airway and assisted ventilation
- Close monitoring by appropriately trained personnel in a setting equipped and staffed for cardiopulmonary resuscitation

For subjects requiring emergency opioid analgesics prior to dosing, the study drug should not be administered. If opioid analgesics are required after the study drug has been dosed, it may take several days for opiate sensitivity to be restored, since samidorphan is an opioid antagonist and could interfere with opioid-mediated pain management.

#### **8.4.5. Other Restrictions and Requirements**

Additional restrictions and requirements include:

- Prohibited substances include amphetamines (including methamphetamine), cocaine, barbiturates, methadone, opioids (including morphine, oxycodone, methadone, and buprenorphine), and phencyclidine

- Subjects will be required to abstain from blood or blood product donation during the study and for 30 days following the follow-up visit
- Subjects will be instructed to maintain their normal caffeine intake and/or tobacco use as well as normal activity/exercise throughout the study. Subjects will be asked to abstain from strenuous physical activity for 48 hours prior to each study visit
- Subjects are prohibited from participating in a weight management program (including weight loss surgery) or from entering a smoking cessation program for the duration of the study

Subjects will be asked to refrain from driving, operating machinery, or engaging in hazardous activities until they and the investigator are sure the study drug is not impairing their judgment and/or ability to perform skilled tasks.

See [Section 8.3.4](#) for details regarding the concomitant medication review.

## **9. TREATMENT OF SUBJECTS**

### **9.1. Study Drug Dose and Administration**

Study drugs include:

- ALKS 3831 10/10 (10 mg olanzapine/10 mg samidorphan) or 20/10 (20 mg olanzapine/10 mg samidorphan) administered as a coated bilayer tablet
- Olanzapine 10 mg or 20 mg administered as a coated bilayer tablet

At Visit 2 and all subsequent visits until Visit 17 (EOT), subjects will be given blister cards containing study drug to take at home. Subjects will be instructed to take one tablet by mouth each day, preferably at bedtime. Dosing may be switched to another time at the investigator's discretion if there are tolerability problems; however, frequent switching is discouraged.

Subjects will be instructed to keep all unused tablets in their blister card and to return unused tablets to the study site at their next visit. If dosing is to occur at that visit, the dose should be taken from the subject's next blister card, not from the card they are returning.

If a dose is missed or forgotten, subjects will be instructed to resume regular dosing the following night. Subjects will be instructed not to take a double dose to try to "make up" for the missed dose.

### **9.2. Study Drug Return and Adherence Review**

Subjects will undergo a study drug adherence review at the timepoints indicated in [Table 3](#). Subjects will be instructed to keep all unused tablets in their original containers and to return the original containers with any unused study drug at each visit following dispensation. Study drug accountability will be documented as the number of tablets dispensed, dosed, lost/missing, or remaining. If applicable, the site will discuss non-adherence with the subject

### **9.3. Randomization/Method of Assigning Subjects to Treatment**

Subjects meeting eligibility criteria at baseline (Day 1) will be randomized in a 1:1 ratio to ALKS 3831 or olanzapine.

Randomization will be performed centrally through an Interactive Web Response System (IWRS). A unique randomization number will be assigned by the IWRS once eligibility has been determined. Once a randomization number has been assigned, that number must not be used again if, for example, a subject is withdrawn from the study. Codes will be prepared by an independent biostatistician who is not otherwise involved in this study.

### **9.4. Blinding**

All Alkermes staff, clinical staff, and subjects will be blinded to treatment assignment until database lock.

The principal investigator is responsible for all trial-related medical decisions. If the investigator deems it necessary to break the study blind in the interest of a subject's medical safety, he or she must make every effort to contact the CRO/sponsor medical monitor before the blind is broken.

If the site is unable to contact the medical monitor prior to breaking the blind, the medical monitor must be contacted within 24 hours following disclosure of study drug assignment. Any premature unblinding should be promptly documented.

Breaking the blind for a single subject will not affect the blind for the remaining subjects.

## **10. STUDY DRUG MATERIALS AND MANAGEMENT**

### **10.1. Study Drug**

The ALKS 3831 drug product will be supplied as a coated bilayer tablet in two fixed-dose combinations:

- ALKS 3831 10/10 (10 mg olanzapine/10 mg samidorphan)
- ALKS 3831 20/10 (20 mg olanzapine/10 mg samidorphan)

Samidorphan is a Schedule II controlled substance. Thus, ALKS 3831 should be treated as a Schedule II controlled substance in the US and any other country in which it is controlled.

Matching olanzapine-only drug will be manufactured by Alkermes, Inc and will be supplied as a coated bilayer tablet in two dose strengths:

- OLZ 10 (10 mg olanzapine)
- OLZ 20 (20 mg olanzapine)

### **10.2. Packaging and Labeling**

ALKS 3831 and olanzapine will be supplied in blister packs. Blister cards will be in weekly and biweekly configurations. Weekly blister cards will contain 9 tablets, enough for 1 week of dosing plus sufficient overage for 2 additional once daily doses. Biweekly blister cards will contain 16 tablets, enough for 2 weeks of dosing plus sufficient overage for 2 additional once daily doses.

### **10.3. Storage**

Product should be stored at not more than 25°C.

Under the US Controlled Substances Act, samidorphan is considered a Schedule II substance because it is derived from opium alkaloids. Therefore, samidorphan and/or blinded study drug must be stored in accordance with restrictions related to Schedule II substances. The site will take adequate precautions, including storage of the investigational drug in a securely locked, substantially constructed cabinet, or other securely locked, substantially constructed enclosure, access to which is limited, to prevent theft or diversion of the substance.

### **10.4. Accountability**

The investigator will be responsible for the oversight of recording the receipt and administration of study drug, and for insuring the supervision of the storage and allocation of these supplies. The investigator is required to maintain current drug dispensing and accountability logs throughout the study. The investigator may delegate accountability duties to an appropriate and qualified pharmacist or staff member who is under the supervision of the investigator. The investigator or designee must allow the Clinical Research Associate or equivalent to perform drug reconciliation during each study monitoring visit. All unused supplies will be checked against the study drug movement records before investigational drug is returned or destroyed.

Refer to [Section 8.3.15](#) for additional study drug reconciliation procedures.

### **10.5. Handling and Disposal**

Following completion and verification of accountability logs, all unused and used packages must be destroyed. Packages may be destroyed on site according to Good Clinical Practice (GCP) and site practice. Alternatively, the sponsor may arrange for destruction with a third party vendor operating in accordance with GCP and/or Good Manufacturing Practice (GMP), as applicable.

## 11. ASSESSMENT OF EFFICACY

The following assessments will be used to collect efficacy throughout the study:

- Weight (Primary Endpoint)

Antipsychotic efficacy measures include the following:

- Positive and Negative Symptom Scale (PANSS)
- Clinical Global Impression – Severity (CGI-S)
- Clinical Global Impression – Improvement (CGI-I)

See [Section 8.3.7](#) and [Section 8.3.9.2](#) for more details on weight measurement and antipsychotic efficacy assessments.

### Other Assessments

- Cigarette Use Questionnaire
- Impact of Weight on Quality of Life – Lite (IWQOL-Lite) Questionnaire
- EuroQol-5D (EQ-5D)
- Substudy: an exploratory substudy will measure body composition (using Bioelectrical Impedance Analysis [BIA]) in subjects at a subset of sites participating in the main ALK3831-A303 study

See [Section 8.3.9.4](#) for more details on the questionnaires and quality of life assessments. See [Addendum A](#) for substudy details.

## **12. ASSESSMENT OF PHARMACOKINETICS AND PHARMACODYNAMICS**

Concentrations of olanzapine, samidorphan, and metabolites of interest will be determined from plasma samples collected according to the schedule in [Table 3](#). Pharmacokinetic (PK) data from these samples may be included in a subsequent population PK analysis conducted outside of this study. By-subject listings of plasma concentrations will be provided.

### 13. ASSESSMENT OF SAFETY

The following assessments will be collected to measure safety and tolerability throughout the study:

- Adverse events (AEs)
- Waist Circumference
- Clinical laboratory parameters including chemistry, hematology, and urinalysis
- Vital signs (oral temperature, respiratory rate, orthostatic blood pressure, and heart rate)
- Electrocardiogram parameters (Uncorrected QT, QTcF, QTcB, PR, RR, and QRS intervals)
- Columbia-Suicide Severity Rating Scale (C-SSRS)
- Abnormal Involuntary Movement Scale (AIMS)
- Simpson-Angus Scale (SAS)
- Barnes Akathisia Rating Scale (BARS)

See [Section 8.3.9.3](#) for more details regarding safety assessment questionnaires.

#### 13.1. Definition of Adverse Event

An AE is any untoward medical occurrence in a patient or clinical investigation subject administered a pharmaceutical product. The occurrence, which may or may not have a causal relationship with the investigational treatment, may include any clinical or laboratory change that does not commonly occur in that subject and is considered clinically significant.

Illnesses present prior to the subject signing the informed consent form (ICF) are considered to be pre-existing conditions and are documented on the medical history eCRF. Pre-existing conditions that worsen during the study are entered on the AE eCRF.

All out-of-range laboratory values will be deemed as clinically significant or not clinically significant by the investigator. Clinically significant values will be considered AEs and recorded as such on the eCRFs.

Pregnancy is not considered an AE, although a subject will be withdrawn from the study if a pregnancy occurs. As described in [Section 8.4.1](#), the pregnancy must be reported to Alkermes and additional follow-up may be required.

#### 13.2. Definition of Serious Adverse Event

An SAE is any AE, occurring at any dose and regardless of causality that meets one or more of the following criteria:

- Results in death
- Is life-threatening. The subject is at immediate risk of death from the reaction as it occurs. This does not include reaction that, had it occurred in a more severe form, might have caused death
- Requires inpatient hospitalization or prolongation of existing hospitalization. Hospital admission for elective surgery scheduled prior to study entry is not considered an SAE
- Results in disability/incapacity (eg, a substantial disruption of a person's ability to conduct normal life functions)
- Is a congenital anomaly/birth defect

Important medical events that may not result in death, be immediately life threatening, or require hospitalization may be considered to be SAEs when, based upon appropriate medical judgment, they may jeopardize the patient or subject and may require intervention to prevent one of the other outcomes listed above.

### **13.3. Relationship to Study Drug**

The assessment of study drug relationship to each AE will be reported on the appropriate source document (and SAE form, in the event of an SAE) by the investigator (or designated sub-investigator) according to his/her best clinical judgment. The criteria listed in [Table 5](#) should be used to guide this assessment. Please note that not all criteria must be present to be indicative of a particular drug relationship. All study drugs are considered "test drugs" for the purposes of the definitions listed in the table.

**Table 5: Adverse Event Causality Guidelines**

Relationship	Criteria for Assessment
Definitely Related	
There is evidence of exposure to the test drug.
 
AND
 
The temporal sequence of the AE onset relative to administration of the test drug is reasonable.
 
The AE is more likely explained by the test drug than by another cause.
 
Dechallenge (if performed) is positive.
 
Rechallenge (if feasible) is positive.
 
The AE shows a pattern consistent with previous knowledge of the test drug or test drug class.

Probably Related	
There is evidence of exposure to the test drug.
 
AND
 
The temporal sequence of the AE onset relative to administration of the test drug is reasonable.
 
The AE is more likely explained by the test drug than by another cause.
 
Dechallenge (if performed) is positive.

Possibly Related	
There is evidence of exposure to the test drug.
 
AND
 
The temporal sequence of the AE onset relative to administration of the test drug is reasonable.
 
The AE could have been due to another equally likely cause.
 
Dechallenge (if performed) is positive.

Probably Not Related	
There is evidence of exposure to the test drug.
 
AND
 
There is another more likely cause of the AE.
 
Dechallenge (if performed) is negative or ambiguous.
 
Rechallenge (if performed) is negative or ambiguous.

Definitely Not Related	
The subject did not receive the test drug.
 
OR
 
Temporal sequence of the AE onset relative to administration of the test drug is not reasonable.
 
OR
 
There is another obvious cause of the AE.

### 13.4. Monitoring and Recording of Adverse Events

Adverse event data collection will begin after a subject signs the ICF and will continue until completion of the final study visit (Visit 19 for subjects completing the study or the final monthly visit for subjects discontinuing study drug, but returning for monthly visits). Any AE or SAE having an onset after the final study visit will not be reported unless the investigator feels that the event may be related to the study drug.

Subjects will be instructed by the investigator or designee to report the occurrence of any AE. All volunteered, elicited, and observed AEs are to be recorded on the AE eCRFs.

The investigator will assess all AEs regarding any causal relationship to the study drug (see [Section 13.3](#)), the intensity (severity) of the event, action taken, and subject outcome.

The following criteria should be used to guide the assessment of intensity (severity):

- **Mild:** Causes awareness of sign or symptom, but is easily tolerated; does not interfere with usual activities
- **Moderate:** Causes discomfort enough to interfere with usual activities
- **Severe:** Is incapacitating; results in inability to work or perform usual activities

All AEs will be followed until resolution, until deemed stable by the investigator, or until the subject is deemed by the investigator to be lost to follow-up.

For clinical study safety reporting purposes, the most recent version of the Investigator's Brochure will be used as the reference document to designate event expectedness.

Withdrawal from the study as a result of an AE and any therapeutic measures that are taken shall be at the discretion of the investigator. If a subject withdraws from the study for any reason, any ongoing AEs will be followed until resolution, until deemed stable by the investigator, or until the subject is deemed by the investigator to be lost to follow-up.

### 13.5. Reporting of Serious Adverse Events

All SAEs must be reported to PPD [REDACTED] within 1 business day of discovery, by emailing: PPD [REDACTED] or faxing the report to the following:

Attention: PPD [REDACTED] Medical Monitor

US Fax Number: PPD [REDACTED]

EU Fax Number: PPD [REDACTED]

The written report should be submitted on the SAE form provided for this purpose. The report must include the investigator's opinion as to whether the event is study drug-related. If this relationship is determined to be possibly, probably, or definitely related to study drug, evidence to support this assessment must also be provided.

## 14. STATISTICS

### 14.1. Sample Size Considerations

The initial target sample size is 200 randomized subjects per treatment group (400 in total). This sample size will provide at least 90% power to detect a significant difference in mean percent change in body weight at Week 24 of 4% or more (3.0% on ALKS 3831 vs 7% on olanzapine group with standard deviation of 9%) and a 13% difference in proportion of subjects with  $\geq 10\%$  weight gain at Week 24 (14% on ALKS 3831 vs 27% on olanzapine group).

An unblinded interim analysis is planned to be conducted to determine if the final sample size will be increased to 540 (270 subjects per treatment group [Section 14.7](#)).

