Olanzapine is regarded as one of the most effective antipsychotic agents with well-recognized efficacy and decreased incidence of extrapyramidal symptoms. However, its efficacy is compromised by safety and tolerability limitations that affect compliance and retention of patients on olanzapine therapy (Lieberman et al, 2005). In particular, results of the Clinical Antipsychotic Trials of Intervention Effectiveness (CATIE), identify olanzapine as an effective atypical antipsychotic associated with the highest weight gain (9.4 kg over a treatment period up to 18 months and  $\geq 7\%$  body weight in 30% of subjects) and a comparatively higher discontinuation rate compared to other antipsychotic agents due to weight gain and metabolic effects. As a result of these limitations surrounding safety, tolerability, adherence and retention, the risk of olanzapine therapy can outweigh the benefit and patients are often switched to alternative antipsychotic agents even if they are less effective.

ALKS 3831 is a fixed-dose combination product of olanzapine and samidorphan (also referred to as ALKS 33 or RDC-0313, see Section 5.2.1 for more information on samidorphan) under investigation for the treatment of schizophrenia. Phase 1 and Phase 2 studies demonstrated that coadministration of samidorphan with olanzapine attenuates the weight gain experienced with olanzapine alone. Results from these studies are described in more detail in Section 5.3. In addition, ALKS 3831 may have the further benefit of controlling substance abuse in patients with schizophrenia. Comorbid substance use disorder is a well-recognized obstacle to patient care. An estimated 1 out of every 3 patients with schizophrenia (33.7%) meet or have met criteria for alcohol use disorder (Regier et al, 1990). Patients with both schizophrenia and alcohol use disorder represent a common variant of the schizophrenia spectrum that is difficult to treat and is associated with an extremely poor prognosis (Dixon 1999; Koekkoek et al, 2006). In clinical studies, samidorphan has been shown to block both the subjective and physiological effects of

the opioid agonist remifentanyl ([ALK33-004](#)) and it is correlated with reduced drinking behavior in adults with alcohol dependence ([ALK33-005](#)). [ALK3831-401](#) is an ongoing clinical study designed to evaluate the effect of ALKS 3831 on drinking behavior in adult subjects with schizophrenia and alcohol use disorder.

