### 14.2. General Statistical Methodology

The statistical analysis methods are described below. Additional details will be provided in the Statistical Analysis Plan (SAP).

In general, summary statistics (n, mean, standard deviation [SD], median, minimum and maximum for continuous variables, and number [%] of subjects in each category for categorical variables) will be provided by treatment group for all variables.

Source data for the summary tables and statistical analyses will be presented as subject data listings.

All statistical tests and confidence intervals, unless stated otherwise, will be 2-sided and will be set at  $\alpha=0.05$ .

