3.8.2.1.1. Primary Analysis

The primary endpoint will be analyzed by analysis of covariance (ANCOVA) with the multiple imputation (MI) method for handling of missing values. Only the on-treatment measurements will be included in the analysis. The following steps will be performed:

1. The missing data on body weight in Stage 1 subjects will be imputed using MI. If there is any subject whose missing data pattern is non-monotonic (defined as having missing data in between visits), the Markov Chain Monte Carlo (MCMC) method will be used to impute the data to a monotonic missing pattern (i.e., if the data is missing at the current visit, the data at all following visits are missing). A single Markov chain will be used with 200 burn-in iterations, 100 iterations between imputations and a Jeffrey's prior. Next, the missing data will be imputed sequentially by each visit using a regression method. The imputation regression model includes treatment group, race (Black or African American, Non-Black or African American) and baseline age (<30, ≥30 years) as factors, and body weight at all previous visits (including baseline weight) as covariates. At least five hundred imputations will be carried out. More imputations may be performed to improve the precision. The initial seed for both steps of the imputation will be 1104078.
2. Percent change from baseline in weight at Week 24 of each of these multiply imputed datasets will be analyzed by the ANCOVA model with treatment group, race (Black or African American, Non-Black or African American), and baseline age (<30, ≥30 years) as factors, and the baseline weight as covariate.
3. Results from Step 2 will be combined using Rubin's method to get the Stage 1 results, including estimated treatment effect, standard error and test statistic z_1 .
4. Repeat Steps 1 to 3 for Stage 2 Subjects. Estimated treatment effect, standard error and test statistic z_2 will be obtained.
5. To adjust for the IA for sample size re-estimation, the independent test statistic from two stages will be combined using the CHW method with a fixed weight of $\sqrt{0.5}$ based on the original sample size (Cui et al, 1999):

$$Z_{chw}^* = \sqrt{t_1}z_1 + \sqrt{1 - t_1}z_2$$

where $t_1 = 200/400$,

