3.8.4. Multiple Comparison/ Multiplicity

The study will be claimed positive when the primary analyses of both co-primary efficacy endpoints are statistically significant based on the CHW method to adjust for the unblinded interim analysis for sample size re-estimation; therefore, both co-primary endpoints will be tested at a full α level of 0.05. A fixed sequence approach will be used to control overall Type I error rate for the primary and key secondary endpoints. Only if both primary endpoints are statistically significant based on the CHW method will the key secondary endpoint be further tested at an alpha level of 0.05.

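### The claim of at least 90% power at 200 randomized per arm holds for the ≥10% weight-gain co-primary only if essentially every subject has an observed Week 24 on-treatment weight

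*Protocol*

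**What the plan says.** Protocol 14.1 sets the target: "The initial target sample size is 200 randomized subjects per treatment group (400 in total"). It continues: "This sample size will provide at least 90% power to detect a significant difference", for a 4-point difference in mean percent weight change (3% vs 7%, SD 9%) and for 14% vs 27% of subjects gaining at least 10%. The synopsis and SAP 2 repeat this. None of the three gives a dropout rate, an evaluable number or an inflation factor, and Protocol 7.4 says that subjects who discontinue after randomization are not replaced.

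SAP 3.8.2.1.1 restricts the data: "Only the on-treatment measurements will be included in the analysis". Missing values are multiply imputed, and SAP 3.8.2.2.1 applies the same rule to the ≥10% endpoint. Weights collected after stopping study drug (Protocol 7.3) enter only a sensitivity analysis.

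On success, SAP 3.8.4 says: "The study will be claimed positive when the primary analyses of both co-primary efficacy endpoints are statistically significant based on the CHW method". Protocol 14.1 and 14.7 also allow an increase to 270 per arm, depending on conditional power at a single interim analysis.

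**The concern.** The power figure is tied to the number randomized, but the analysis observes only those still on drug with a Week 24 weight. Imputation recovers part of what the others would have contributed, not all of it. Because both endpoints must be significant, joint power cannot exceed that of the weaker one, the ≥10% endpoint. If that endpoint only just reaches 90% with complete data, the claim depends on a condition that the documents do not state.

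Some discontinuation is plainly expected over 24 weeks. The protocol schedules monthly weight visits for subjects who stop drug, and its Background describes olanzapine as having "a comparatively higher discontinuation rate compared to other antipsychotic agents due to weight gain and metabolic effects". That is a comparison with other drugs over up to 18 months, not a rate for this trial.

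What is at stake is how the design is described and how a narrow miss on the binary co-primary would be read. Type I error and the validity of the analysis are not affected.

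**Working it through.** **Inputs.** Two-sided α = 0.05 (Protocol 14.2); each co-primary is tested at the full level (SAP 3.8.4: "both co-primary endpoints will be tested at a full α level of 0.05"); 1:1 allocation (Protocol 9.3); n = 200 per arm; 14% vs 27%; 3% vs 7% with SD 9 (Protocol 14.1).

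**Step 1: reproduce the stated figure, complete data.**

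- Percent change: Φ[4 / (9√(2/200)) − 1.96] = Φ(4.444 − 1.960) = Φ(2.484) = 99.4%.
- ≥10% gain. The mean proportion is (0.14 + 0.27)/2 = 0.205. SE under the null = √(2 × 0.205 × 0.795/200) = 0.04037. SE under the alternative = √((0.14 × 0.86 + 0.27 × 0.73)/200) = 0.03984.
  - Pooled: Φ[(0.13 − 1.96 × 0.04037)/0.03984] = Φ(1.277) = 89.9%.
  - Unpooled: Φ[0.13/0.03984 − 1.96] = Φ(1.303) = 90.4%.
  - Other versions: exact power of the chi-square test 90.4%, arcsine 90.3%, Wald test on the log odds ratio 88.7%.

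The stated 90% therefore reproduces.

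**Step 2: the reserve.** Unpooled power is 90.2% at 199 per arm, 90.1% at 198 and 89.9% at 197. The slack is 2 subjects per arm, or 1%. Under the pooled formula there is none, since 201 per arm are needed for 90%.

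**Step 3: joint power, complete data.** With the pooled formula and an assumed correlation of 0 to 0.8 between the endpoints, joint power is 89.3% to 89.9% at 200 per arm.

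**Step 4: dropout at a fixed 200 per arm.** The rates are assumptions. The completer-only column treats dropouts as contributing nothing and uses n = 200(1 − d); it is a lower bound. The multiple-imputation column combines two simulations that share sequential-regression imputation, 20 imputations, Rubin's rules and dropout unrelated to weight.

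| Dropout | n completing per arm | ≥10% gain, completers only (pooled–unpooled) | ≥10% gain, multiple imputation (simulated) |
|---|---|---|---|
| 10% | 180 | 86.6–87.2% | about 88–89% |
| 20% | 160 | 82.4–83.1% | about 85–89% |
| 30% | 140 | 77.2–77.9% | about 84–87% |
| 40% | 120 | 70.6–71.5% | about 81–86% |

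The lower ends come from a simulation with Brownian-type correlation between visits (88.0, 85.4, 84.5 and 81.0%). Its power for both endpoints together was 88.0, 85.3, 84.3 and 80.9%. The second simulation used two correlation structures and gave 88.8–89.4, 86.2–88.8, 84.8–87.0 and 83.6–86.4% for the ≥10% endpoint alone, which caps joint power. Its Monte Carlo error is about 1 point and its complete-data runs ranged over 89–91%, so its upper values at 10% and 20% dropout cannot be separated from 90% by simulation alone. Percent change keeps 93.1% power with completers only at 40% dropout.

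**Step 5: add the interim rule.** Assumptions: conditional power under the observed trend (the interim analysis plan is a separate document), endpoint correlation 0.6, unpooled variance, fixed weights √0.5, the 30% and 90% zone limits, 270 per arm if triggered, and 1,000,000 simulated trials per row.

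| Information lost | Joint power, fixed 200 | Joint power, with interim rule |
|---|---|---|
| 0% | 90.2% | 92.9% |
| 5% | 88.7% | 91.6% |
| 10% | 86.8% | 90.1% |
| 15% | 84.8% | 88.4% |
| 20% | 82.4% | about 86.5% |

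The increase was triggered in about 30% of simulated trials. These rows are losses of information, which are smaller than dropout rates because imputation recovers part of each dropout's contribution.

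**The case against.** **The figure is right as calculated.** This stands. With complete data 90% reproduces, so a reader who infers a calculation error would be mistaken. What is missing is the condition.

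**The design is adaptive.** A reader might infer that any dropout puts the trial as a whole below 90%. The documents do not support that. At fixed size, the unpooled formula tolerates 2 lost subjects per arm. With the interim rule, joint power stays at about 90% or more up to roughly 10% information loss, on the assumptions in Step 5. On the other side, the quoted sentence concerns the initial 200 per arm, the increase is conditional, and no section offers it as cover for dropout.

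**The dropout figures depend on the model.** This also stands. The rate, the correlation between visits and the unrelatedness of dropout to weight are all assumed. The simulations keep 14% vs 27% and therefore cannot also keep means of 3% and 7% with SD 9 under a normal model: those values would imply 21.8% vs 36.9% and power of 91.6–92.0%. The plan states 14% vs 27%, so its claim is judged on those rates, but no single simulated value should be printed as the replacement. Covariate adjustment might help; the documents claim no such gain.

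**The Background gives no discontinuation rate.** Correct. It supports expecting some dropout, not a particular amount.

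**Conclusion.** The point holds as a missing condition on a stated number. With all 200 per arm observed, the ≥10% endpoint has 89.9% (pooled) to 90.4% (unpooled) power, and it is below 90% once more than about 1% of the information is lost. At a fixed 200 per arm, joint power is therefore below 90% at any realistic dropout: by roughly 1–2 points at 10%, 1–5 at 20%, 3–6 at 30% and 4–9 at 40%, with multiple imputation and the assumptions above.

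Two limits apply. Percent change in weight is not at risk. And the conditional increase to 270 per arm may bring joint power back to about 90% if no more than about 10% of the information is lost. A reader might also infer that the trial is too small or its analysis unsound; neither follows from this point.

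**What to change.** Keep the sample size and the analysis. In Protocol 14.1, the synopsis and SAP 2:

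- State that 200 per arm gives about 90% power for the ≥10% endpoint, and for both co-primaries jointly, with complete Week 24 on-treatment data.
- Give the sponsor's expected dropout rate and the joint power under it with the planned multiple-imputation analysis, once at a fixed 200 per arm and once with the interim sample-size rule included.
- If the interim increase is meant to absorb dropout, say so.

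The cost is a change of wording in three places and one simulation by the sponsor. The stated power becomes slightly less favourable at fixed size. No extra patients are needed.
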